	 Change from baseline in the number of monthly days with use of acute migraine medication Change from baseline in the number of monthly migraine days with use of acute migraine medication PGIC score Change from baseline in the number of monthly migraine days in patients with MOH MBS score Change from baseline in monthly number of Migraine attacks for each 12-week period Change from baseline in monthly number of Headache episodes for each 12-week period Change from baseline in the MSQ v2.1 sub-scores Change from baseline in the EQ-5D-5L VAS score HCRU Change from baseline in the WPAI sub-scores
 Safety Objective To evaluate the safety and tolerability of eptinezumab To evaluate the long-term safety and tolerability of eptinezumab 	 Safety Endpoints Adverse events Absolute values and changes from baseline in clinical safety laboratory test values, vital signs, weight, and ECG parameter values Potentially clinically significant clinical safety laboratory test values, vital signs, weight changes, and ECG parameter values Development of specific anti-eptinezumab antibodies (ADA) including neutralizing antibodies (NAbs) Columbia-Suicide Severity Rating Scale (C-SSRS) score

2 Study Design

This is an interventional, multi-national, multi-site, randomized, double-blind, placebocontrolled Phase IIIb study designed to demonstrate efficacy and safety of eptinezumab for migraine prevention in patients with unsuccessful prior preventive treatments. The placebocontrolled period will be followed by an extension period where all patients will receive active treatment to assess the long-term safety, tolerability and effect of eptinezumab.

The target population for this study is defined as patients with chronic migraine (CM) or episodic migraine (EM), as outlined in the IHS ICHD-3 guidelines¹ with documented evidence of migraine occurring on \geq 4 days per month prior to screening as confirmed via prospectively collected information in the eDiary during the Screening Period, and with documented evidence of failure to 2-4 different preventive migraine medications in the past 10 years. The aim is that approximately 40% of the randomized patients are patients with EM.

It is planned that 840 patients will be randomly allocated to one of three treatment groups: eptinezumab 300 mg, eptinezumab 100 mg, or placebo, in a ratio of 1:1:1.

Randomization will be stratified by country and monthly headache days (MHDs) at baseline (\leq 14 MHDs/>14 MHDs).

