12.4.2 Analysis of the Key Secondary Endpoints

50% and 75% response

The two key secondary endpoints, 50% response (Weeks 1-12) and 75% response (Weeks 1-12) will be analysed using logistic regression. The model will include baseline MMDs as a continuous covariate, and treatment and stratification factor (MHDs at baseline: $\leq 14 />14$) as factors. The SAS[®] code for these key secondary analyses is shown in Appendix IV.

The logistic regression model will be fitted using the maximum likelihood (ML) method and the logit link function.

The odds ratios for eptinezumab 300 mg and eptinezumab 100 mg compared to placebo will be estimated from the model and presented with p-values based on the likelihood ratio test and 95% CIs based on the profile likelihood.

The nominal p-values comparing each dose of eptinezumab to placebo will be presented. The comparisons will be part of the testing strategy described in Section 12.2.

In addition, the differences in response proportions between each dose of eptinezumab and placebo will be presented.

Change from Baseline in the number of MMDs (Weeks 13-24)

Changes from Baseline in MMDs at Weeks 1-4, Weeks 5-8, Weeks 9-12, Weeks 13-16, Weeks 17-20, and Weeks 21-24 will be analysed using the same methodology as described in Section 12.3.2 for the primary endpoint.

The mean differences between each dose of eptinezumab and placebo will be estimated based on the least squares means for the treatment-by-visit interaction in the MMRM model. The estimates will be presented with nominal p-values and 95% CIs. The comparisons will be the contrasts between each dose of eptinezumab and placebo averaged across Weeks 13-24. The comparisons will be part of the testing strategy described in Section 12.2.

Change from Baseline in HIT-6

Changes from Baseline in HIT-6 total score at weeks 4, 8, 12, 16, 20, and 24 will be analysed using the same methodology as described in Section 12.3.2 for the primary endpoint, replacing baseline MMD score with baseline HIT-6 score in the model.

The mean differences between each dose of eptinezumab and placebo will be estimated based on the least squares means for the treatment-by-visit interaction in the MMRM model. The estimates will be presented with nominal p-values and 95% CIs. The comparisons will be the contrasts between each dose of eptinezumab and placebo at Week 12. The comparisons will be part of the testing strategy described in Section 12.2.

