12.4.3 Rationale for Selected Analysis Method for the Key Secondary Endpoints

The rationale for the selected analysis method for change from Baseline in the number of MMDs (Weeks 13-24) and change from Baseline in HIT-6 is covered by Section 12.3.4.

The logistic regression model has been chosen for its ability to provide estimates of treatment effects, as well as adjust for the effects of strata and covariates. Covariates are included in the model based on an approach including key factors representing study design features/strata (stratum and treatment), and baseline MMDs to account for its predictive ability for the response.

Although it is recognized that adjustment for predictive covariates will always, in contrast to classical linear regression models, result in a loss of precision (or no change) of the estimates, the adjustment for predictive covariates will result in greater efficiency/higher power when testing for a treatment effect in a randomized study.^{2,3} The chosen covariate is considered to

be highly predictive for the response, and thus the logistic regression model is considered valid as a key secondary analysis model.

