12.5 Analysis of the Secondary Endpoints

The following endpoints will be derived according to the descriptions given in Section 19.1 and analysed using the same methodology as that described for the primary endpoint (see Section 12.3.2) with a few exceptions, which are highlighted below the list:

- Change from baseline in the number of MHDs (Weeks 1-12)
- Change from baseline in percentage of migraine/headaches with severe pain intensity (Weeks 1- 12)
- Change from baseline in the number of MMDs with use of acute medication (Weeks 1- 12 and Weeks 13-24)
- Change from baseline in the number of monthly days with use of acute migraine medication (Weeks 1-12 and Weeks 13-24)
- PGIC score at Week 12 and at Week 24
- Change from baseline in the number of MMDs in patients with MOH (Weeks 1-12)
- MBS score at Week 12
- Change from baseline to Week 24 in the HIT-6 score

- Change from baseline to Week 12 and to Week 24 in MSQ v2.1 sub-scores (Role Function-Restrictive, Role Function-Preventive, Emotional Function)
- Change from baseline to Week 12 and to Week 24 in EQ-5D-5L VAS score
- Change from baseline to Week 12 and to Week 24 in WPAI sub-scores (Absenteeism, Presenteeism, Work productivity loss, Activity impairment)

For the endpoints listed above, the baseline MMD score will be replaced with the baseline score for the endpoint in question in the model except for analysis of PGIC and MBS, which will exclude the baseline score terms, since the rating of the scales in themselves represent a change from baseline so no baseline score exists.

In the analysis of MHDs, the model will include following fixed effects: month, country, and treatment as factors, baseline MHDs as a continuous covariate, treatment-by-month interaction, and baseline score-by-month interaction.

The analysis of MMDs in patients with MOH will only be performed if the number of patients with MOH constitutes a sufficiently large part of the study population.

For HIT-6, in addition to summary tables presenting descriptive statistics for the total score, tables presenting the counts and percentages of patient in each life impact category as defined in Section 19.1.4 will be produced by visit and treatment group.

The following endpoints will be analysed using the same methodology as that described for the key secondary response endpoints (see Section 12.4.2):

- Response: Patients with 50% reduction from baseline in MMDs (Weeks 13-24)

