- Response: Patients with 75% reduction from baseline in MMDs (Weeks 13-24)
- Response: Patients with 50% reduction from baseline in MHDs (Weeks 1-12)
- Response: Patients with 75% reduction from baseline in MHDs (Weeks 1-12)
- Response: Patients with a 5-point reduction from baseline to Week 12 and from baseline to Week 24 in HIT-6

For the HIT-6 response endpoints, LOCF will be used to impute a potentially missing value at Week 12 or Week 24. Baseline values will not be carried forward.

The following endpoints:

- Response: Patients with 100% reduction from baseline in MMDs (Weeks 1-12)
- Response: Patients with 100% reduction from baseline in MHDs (Weeks 1-12)
- Patients with a migraine on the day after first dosing

Will be derived according to the descriptions in Section 19.1.1.2 and 19.1.1.3 and analysed using an extended Cochran-Mantel-Haenszel (CMH) test, adjusting for one of the stratification factors (MHDs at baseline: $\leq 14 /> 14$). The rates for each dose of eptinezumab and placebo will be presented. The SAS[®] code for performing the extended CMH test is shown in Appendix IV.

Descriptive tables displaying the distribution of answers to the items in HCRU at each visit will be provided by treatment group.

Tables displaying the counts and percentage of answers to each category of response options for each item of EQ-5D-5L will be presented by visit and treatment group. Furthermore, shift tables displaying for each item in EQ-5D-5L the number and percentage of patients who decreased, increased or had no change from baseline in the item score will be provided by visit and treatment group.

For inclusion into the *addendum CSR*, the endpoints listed below will be derived according to the descriptions given in Section 19.1 and the absolute values will be analysed using an MMRM similar to the one described for the primary endpoint (see Section 12.3.2) but using treatment sequence group instead of treatment group.

No treatment comparisons will be performed for any of the efficacy endpoints after Week 24. Instead, the estimated mean values will be reported with two-sided 95% confidence intervals by treatment sequence for:

- Number of MMDs (at Weeks 1-4, Weeks 5-8, Weeks 9-12, Weeks 13-16, Weeks 17-20, Weeks 21-24, Weeks 25-36, 37-48, 49-60, and 61-72)
- HIT-6 score (at week 4, 8, 12, 16, 20, 24, 36, 48, 60, and 72)

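### The HIT-6 5-point responder models adjust for baseline migraine days, not baseline HIT-6, which may cost some power (minor, nearly free to improve)

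*SAP*

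**What the plan says.** SAP 12.4.2 defines the logistic model for the 50% and 75% migraine-day responders: "The model will include baseline MMDs as a continuous covariate, and treatment and stratification factor", the factor being baseline monthly headache days (MHDs) at ≤14 or >14.

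SAP 12.5 then has two lists. The first holds the continuous endpoints, analysed by MMRM, and is followed by the rule "For the endpoints listed above, the baseline MMD score will be replaced with the baseline score for the endpoint in question in the model". The second list comes after that rule and opens with "The following endpoints will be analysed using the same methodology as that described for the key secondary response endpoints (see Section 12.4.2". Among its entries is "Response: Patients with a 5-point reduction from baseline to Week 12 and from baseline to Week 24 in HIT-6". The only special instruction for the HIT-6 responders is that a missing Week 12 or Week 24 value is filled by LOCF, without carrying baseline forward. No covariate is named for them.

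For the continuous change in HIT-6, SAP 12.4.2 explicitly puts baseline HIT-6 in place of baseline MMDs. SAP 12.4.3 justifies the logistic model's covariate on the ground that "the adjustment for predictive covariates will result in greater efficiency/higher power when testing for a treatment effect in a randomized study". SAP 18 records that the HIT-6 responder endpoints and their logistic analyses were added after the protocol. Protocol 16.8.7 says only that response variables are analysed in a similar way to the key secondary responses.

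**The concern.** Read literally, the own-baseline rule does not reach the responder list. The HIT-6 responder model therefore contains baseline MMDs and the MHD stratum but not the baseline of the score whose change defines response.

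Whether a patient falls by at least 5 points is likely to depend on where that patient starts. Regression to the mean acts over the whole range. The scale also has a floor of 36 (SAP 19.1.4), so a patient who starts below 36 + 5 = 41 cannot respond at all. SAP 12.4.3 argues that baseline MMDs predict migraine-day response; it offers no such argument for a HIT-6 response. Randomisation is stratified by country and baseline MHDs (SAP 2), so baseline HIT-6 is not balanced by design either.

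At stake is some efficiency in two secondary analyses. There is also a question of exact specification: one reader would fit baseline MMDs and another, following the pattern of the continuous analyses, would fit baseline HIT-6. They would report different odds ratios and p-values for the same endpoint.

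**Working it through.** **1. The plan's own power figure.** The documents state no power for the HIT-6 responders, so the primary endpoint is used to check the sample-size inputs (Protocol 16.10, SAP 16).
- Evaluable patients per arm: 280 × 0.98 = 274.4.
- Effect, 100 mg: 0.4 × 0.69 + 0.6 × 2.03 = 1.494. Effect, 300 mg: 0.4 × 1.11 + 0.6 × 2.60 = 2.004.
- SD: √(0.4 × 3.1² + 0.6 × 5.8²) = √24.028 = 4.90.
- Two-sided 5% power: 94.6% and 99.8%, against the stated 94% and 99%. A 10,000-run simulation of the 40/60 mixture gives 94.5% and 99.8%. The inputs reproduce, so 274 per arm is used below.

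**2. When baseline HIT-6 matters.** If SD_b and SD_f are the baseline and follow-up SDs and r is their correlation, the fall in HIT-6 regresses on baseline with slope 1 − r × SD_f / SD_b. A slope near zero means that baseline carries almost no information on the fall. A steep slope means it carries a lot. The documents give none of these quantities.

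**3. HIT-6 responder, first simulation.** 1,500 trials per row, logistic likelihood-ratio test of treatment at two-sided 0.05. Assumed: SD_b 5; mean fall 3 points on placebo and 5 on active (4.5 where SD_f is 5). Baseline MMDs are given no effect beyond their correlation with baseline HIT-6. Both models contain the stratum.

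| SD_f | r | HIT-6/MMD correlation | Slope | Baseline/response correlation | Power, baseline MMDs | Power, baseline HIT-6 | Difference (points) |
|---|---|---|---|---|---|---|---|
| 7 | 0.7 | 0.2 | 0.02 | 0.01 | 95.9% | 95.7% | −0.2 |
| 8 | 0.6 | 0.2 | 0.04 | 0.03 | 83.3% | 83.5% | +0.2 |
| 7 | 0.5 | 0.2 | 0.30 | 0.19 | 85.4% | 86.8% | +1.4 |
| 7 | 0.5 | 0.5 | 0.30 | 0.19 | 85.5% | 86.8% | +1.3 |
| 7 | 0.3 | 0.2 | 0.58 | 0.31 | 73.5% | 77.7% | +4.2 |
| 5 | 0.5 | 0.2 | 0.50 | 0.39 | 78.4% | 85.7% | +7.3 |
| 5 | 0.3 | 0.2 | 0.70 | 0.47 | 66.1% | 76.1% | +10.0 |

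Response was 35–39% on placebo and 46–50% on active. Simulation error is about 1 point per power figure and smaller for the paired differences. A model with both baselines gave power within 0.4 points of the baseline HIT-6 model in every row.

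**4. HIT-6 responder, second simulation.** 2,000 trials per setting. Assumed: baseline SD 5, residual SD 7, effect 1.7 points. For slopes 0.3, 0.5 and 0.7:
- HIT-6/MMD correlation 0.2: 61%, 57%, 52% with baseline MMDs; 62%, 60%, 57% with baseline HIT-6.
- Correlation 0.4: 61%, 59%, 55% against 61%, 61%, 60%.

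The gain here is 0 to 5 points.

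**5. Headache-day responders, same comparison.** Assumed: MHD/MMD baseline correlation 0.6–0.9, log-odds slope −0.3 to −1.0 per SD of baseline MHDs, treatment log-odds ratio 0.6, placebo response 24–27%. Power with baseline MMDs, then with baseline MHDs: 89.3% and 89.5%, 86.5% and 86.8%, 87.9% and 88.3%, 83.3% and 84.0%, 87.4% and 87.1%. The change is −0.3 to +0.7 points, which is below the simulation error of a single power figure.

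**The case against.** The strongest reply is that nothing confirmatory depends on this. The HIT-6 responders are outside the sequence in SAP 12.2 and carry nominal p-values under SAP 12.1. The HIT-6 result that is formally tested, change at Week 12, already uses baseline HIT-6. Leaving out a baseline covariate does not invalidate a randomised comparison. All of that stands, and it is why the point is minor.

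A second reply concerns intent. The protocol's wording is loose enough to allow an endpoint-specific baseline, and the MMRM code in SAP Appendix IV uses a generic baseline variable. The logistic code there could not be read in the copy available, so it may do the same. This also stands as a doubt, but that code is headed as serving the 12.4.2 analyses, and the text of 12.5 should settle the matter without it.

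Three stronger readings are tempting and not supported:
- *The same flaw costs power for the headache-day responders.* Baseline MHDs are already in that model as the stratum, and baseline MMDs are a close proxy. Step 5 shows a change under 1 point.
- *The odds ratio is biased towards 1.* An odds ratio adjusted for less is a different conditional quantity, because odds ratios are not collapsible. SAP 12.4.3 itself notes that adjustment in a logistic model costs precision of the estimate while raising the power of the test.
- *Power is certainly lost, because baseline HIT-6 is the main predictor.* The documents contain no figure that shows this.

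**Conclusion.** The point holds as a minor, nearly free improvement to the HIT-6 5-point responder analyses only. As written, 12.5 leaves a collected and plausibly predictive baseline out of the model, against the SAP's own reason for adjusting.

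The likely cost is about 0 to 10 percentage points of power. It is close to zero if the fall in HIT-6 hardly depends on baseline, about 4 points at a baseline/response correlation of 0.31, and about 10 at 0.47. The range rests on assumed SDs, correlations and effects, and the larger simulated range on the further assumption that baseline MMDs add nothing beyond baseline HIT-6. In no setting did the change lose more than 0.2 points, which is within simulation error. The validity of the comparison, the type 1 error of the testing strategy and the stated powers are untouched.

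**What to change.** Add to the responder list in SAP 12.5: *For the HIT-6 response endpoints, baseline MMDs is replaced by baseline HIT-6 total score; treatment and the MHD stratum are kept.* Leave the MMD and MHD responder models as they are. Check that the logistic code in Appendix IV agrees.

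The cost is one sentence and no new data. If the sponsor thinks baseline MMDs may predict HIT-6 response in their own right, keeping both baselines cost at most 0.4 points of power in the simulation.

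The sentence has to be in place before unblinding to count as pre-specified. The list of changes in Protocol Edition 3.0 reports that sponsor staff reviewing the study report were unblinded after the lock of the placebo-controlled period. If that came first, the model as written should stay the planned analysis, and the version with baseline HIT-6 should be reported beside it, labelled as supplementary.

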12.1 General Efficacy Analysis Methodology

Unless otherwise specified, all the efficacy analyses for the Placebo-controlled Period will be based on the FAS and all the efficacy analyses for the Extension Period will be based on the FAS_LT.

All the tables and graphs will be presented by treatment group for the Placebo-controlled Period and both by treatment group and treatment sequence group for the Extension Period.

All the p-values will be based on two-sided tests; the confidence intervals (CIs) will be twosided; and the endpoints not included in the testing strategy will be presented with nominal pvalues and 95% CIs.

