12.2 Testing Strategy

The testing strategy will be a sequence of tests, either testing one endpoint at a time or using Bonferroni-Holm to test a group of endpoints. Only if one step has shown a statistically significant effect will the formal testing continue with the next step, thus ensuring protection of the type 1 error. The steps are described below. A graphical representation of the testing strategy can be found in Panel 3.

A significance level of 0.05 will be used. The significance level is denoted by α below.

Step 1

Test the primary endpoint change from baseline in MMDs (Weeks 1-12) for the 300 mg dose compared to placebo on a significance level of α . Only if the p-value $<\alpha$ in favour of the 300 mg dose is the effect considered statistically significant and the testing continues with the next step.

Step 2

Test the key secondary endpoint 50% responders for MMD (Weeks 1-12) for the 300 mg dose compared to placebo, using a significance level of α . Only if the p-value $<\alpha$ in favour of the 300 mg dose is the effect considered statistically significant and the testing continues with the next step.

Step 3

Test the primary endpoint change from baseline in MMDs (Weeks 1-12) for the 100 mg dose compared to placebo on a significance level of α . Only if the p-value $<\alpha$ in favour of the 100 mg dose is the effect considered statistically significant and the testing continues with the next step.

Step 4

Test the key secondary endpoint 50% responders for MMD (Weeks 1-12) for the 100 mg dose compared to placebo, using a significance level of α . Only if the p-value $<\alpha$ in favour of the 100 mg dose is the effect considered statistically significant and the testing continues with the next step.

Step 5

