For patients with any post-baseline suicidal ideation or behaviour in the Placebo-controlled Period (C-SSRS scores of 1 to 10), listings will be provided based on APRS including all C-SSRS scores prior to entering the Extension Period for those patients for inclusion in the *CSR*.

A similar listing will be provided for patients with any post-baseline suicidal ideation or behaviour in the Extension Period including all the C-SSRS scores for those patients for inclusion in the *addendum to CSR*.

14 Blinded Data Reviews

The quality of the study will be overseen by performing blinded data reviews during the conduct of the study. The reviews may include, but are not limited to, data quality, protocol adherence, and the appropriateness of design assumptions, including the sample size assumptions.

An independent Safety Data Monitoring Committee (DMC) will regularly monitor the patients' safety data according to the *DMC Charter*. The DMC will have access to unblinded information for the double-blind treatment for each patient. Members of the DMC will not be involved in other study-related tasks.

15 Interim Analyses

See Section 18.

16 Sample Size Considerations

The two prior eptinezumab Phase III studies, PROMISE-1 performed in an EM population and PROMISE-2 performed in a CM population, had the following effect sizes for the primary endpoint when compared to placebo (standard deviations):

- EM: 100 mg 0.69 (3.1), 300 mg 1.11 (3.1)
- CM: 100 mg 2.03 (5.8), 300 mg 2.60 (5.8)

The power was determined by simulating the testing strategy (10000 simulations) assuming normal distributions with similar mean and SD for continuous endpoints and similar success rates as the response variables in the Phase III studies for the corresponding population (EM or CM) without assuming the variables to be correlated. With 280 patients per treatment group, assuming that 40% of the patients will be from the EM population and 60% from the

CM population, and that 2% of the patients not having a post-baseline assessment of the primary endpoint, simulations show that the power for the test of the primary endpoint is approximately 94% for the comparison of 100 mg to placebo and 99% power for the comparison of 300 mg to placebo. The individual key secondary endpoints had a power of at least 68% for showing an effect, with a combined power of 58% for seeing an effect for all primary and key secondary endpoints and both doses in the testing strategy.

17 Statistical Software

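### Day-after-dosing migraine, PGIC and MBS are analysed without continuous baseline migraine days, and the Day 1 analysis specifies no effect estimate or CI method

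*SAP*

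**What the plan says.** **Day-after-dosing migraine.** SAP section 12.5 has this endpoint, together with the 100% responders, "analysed using an extended Cochran-Mantel-Haenszel (CMH) test, adjusting for one of the stratification factors", namely baseline MHDs at most 14 or above 14. Protocol section 16.8.7 agrees. The SAS code in SAP Appendix IV crosses stratum, treatment and outcome with no other adjustment, and outputs the row-mean-score p-value separately for each dose. Section 12.5 adds that the rates per arm will be shown. Under SAP section 19.1.1.3 a patient scores 0 or 100 on Day 1. If the diary is missing that day, the score is 100 times Weeks 1-4 MMDs divided by 28.

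**PGIC and MBS.** The endpoint's own baseline replaces baseline MMDs in the primary-type MMRM, "except for analysis of PGIC and MBS, which will exclude the baseline score terms". The reason given is that these scales are themselves ratings of change.

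**Elsewhere in the SAP.** Baseline MMDs come from the 28-day screening diary (section 4.2). They are a continuous covariate in the primary model (12.3.2) and in the 50%/75% responder logistic models (12.4.2). Section 12.4.3 defends the latter on the ground that "the adjustment for predictive covariates will result in greater efficiency/higher power when testing for a treatment effect in a randomized study". Section 12.1 says endpoints outside the testing strategy will be shown with nominal p-values and 95% CIs.

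**The concern.** The MHD stratum is a coarse stand-in for migraine frequency. By the eligibility criteria, episodic patients have roughly 4 to 14 migraine days in 28 and chronic patients roughly 8 to 28. If the chance of migraine on a given day is about MMDs/28, it runs from 14% (4/28) to 50% (14/28) in one stratum and from 29% (8/28) to 100% in the other. The CMH test uses none of that within-stratum spread, and it leaves a chance imbalance in baseline frequency uncorrected.

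For PGIC and MBS, the absence of an own baseline explains why that term goes. It does not explain why baseline MMDs could not take its place.

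A second gap does not depend on power. For Day 1 the SAP specifies rates and a p-value, but no treatment-effect estimate and no method for the interval that section 12.1 promises. Protocol section 1.2 says that onset of effect will be explored with early timepoints, so readers will want an estimate with its uncertainty.

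**Working it through.** **1. Inputs from the documents.** "A significance level of 0.05 will be used" (SAP 12.2). "All the p-values will be based on two-sided tests" (SAP 12.1). "With 280 patients per treatment group", "assuming that 40% of the patients will be from the EM population", the rest chronic, and "2% of the patients not having a post-baseline assessment of the primary endpoint" (SAP section 16). This gives 280 × 0.98 = 274.4 evaluable patients per arm.

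**2. The plan's own power figure.** For the primary endpoint:
- 100 mg difference: 0.4 × 0.69 + 0.6 × 2.03 = 1.494
- 300 mg difference: 0.4 × 1.11 + 0.6 × 2.60 = 2.004
- SD: √(0.4 × 3.1² + 0.6 × 5.8²) = 4.902

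A two-sided 5% comparison of means gives 94.6% and 99.8%, against the stated 94% and 99%. A 10,000-run simulation gives the same. The stated power reproduces and is untouched by this point. The documents state no power for Day 1 migraine, PGIC or MBS.

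**3. Day 1 migraine.** The documents give no baseline distribution or Day 1 effect, so everything here is assumed: mean baseline MMDs of 9 (episodic) and 17 (chronic), and Day 1 probability of MMDs/28. The placebo rate is then (0.4 × 9 + 0.6 × 17)/28 = 13.8/28 = 49%. Within-stratum SDs and the relative reduction were varied. With 274 per arm (110 episodic, 164 chronic) and 3,000 simulated trials per setting, power was as follows.

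| SD episodic/chronic | Reduction | Stratified CMH | Logistic LRT, stratum + baseline MMDs | Gain (points) |
|---|---|---|---|---|
| 2 / 3 | 20% | 65.7% | 68.2% | 2.5 |
| 2 / 3 | 25% | 85.8% | 86.7% | 0.9 |
| 2 / 3 | 30% | 94.8% | 95.6% | 0.8 |
| 3 / 5 | 20% | 67.9% | 71.6% | 3.7 |
| 3 / 5 | 25% | 84.7% | 87.5% | 2.8 |
| 3 / 5 | 30% | 95.4% | 96.9% | 1.5 |
| 3.5 / 7 | 20% | 67.2% | 72.4% | 5.2 |
| 3.5 / 7 | 25% | 85.6% | 89.5% | 3.9 |
| 3.5 / 7 | 30% | 96.0% | 97.7% | 1.7 |

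With no effect, CMH rejected in 4.8-5.5% of trials and the logistic test in 5.3-6.0%, so part of the apparent gain may be test size. The simulation used complete 0/1 outcomes. A separate check of the linear model with robust standard errors, also under assumed baselines, gave a standard error about 3-5% smaller and 2-3 more power points at 20-25% reduction, with type I error near 5%.

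**4. The same loss seen as chance imbalance.** The standard error of the between-arm baseline difference within strata is √(0.4 s₁² + 0.6 s₂²) × √(2/274):
- SD 2/3: 2.65 × 0.0854 = 0.23 MMDs
- SD 3/5: 4.31 × 0.0854 = 0.37
- SD 3.5/7: 5.86 × 0.0854 = 0.50

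Multiplying by 1.96/28 gives a 95% range for the resulting shift in the Day 1 difference of about ±1.6, ±2.6 and ±3.5 percentage points. A 20% reduction from 49% is about 10 points. This is random error that adjustment would remove. It is not bias, and it is not additional to step 3.

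**5. PGIC and MBS.** If r is the within-stratum correlation with baseline MMDs, the standard error shrinks by √(1 − r²). Starting from an assumed 70% power:
- r = 0.1: factor 0.995, power 70.4%
- r = 0.2: factor 0.980, power 71.8%
- r = 0.3: factor 0.954, power 74.0%
- r = 0.5: factor 0.866, power 81.8%

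The documents give no value of r.

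**The case against.** The best defence is that the planned analyses are coherent. All three endpoints assigned to CMH can take non-binary values: Day 1 through the imputed fractions, and the 100% responder rate through values such as 0.67. The row-mean-score statistic accepts these and binary logistic regression does not, whereas the 50%/75% responders are strictly 0/1. For PGIC and MBS the SAP follows its rule that each scale uses its own baseline; HIT-6, MSQ, EQ-5D VAS and WPAI do not carry baseline MMDs either. Randomisation keeps the tests valid, and no formal conclusion depends on them.

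Most of this stands. It rules out plain logistic regression as the remedy and any suggestion that the Day 1 endpoint was simply overlooked when the responder analyses changed. It does not explain why a covariate already in hand is left out of a linear model, which takes fractional scores.

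Three stronger readings are tempting and unsupported:
- **No baseline adjustment at all.** All three analyses adjust for the baseline MHD stratum, and PGIC and MBS also keep country and stratum-by-month.
- **The SAP itself regards baseline MMDs as strongly predictive of these endpoints.** Section 12.4.3 says so only of the 50%/75% response. Extending it to Day 1 migraine is a reasonable inference; for PGIC and MBS nothing documents it.
- **No interval is planned for Day 1.** Section 12.1 does promise one; what is missing is the estimate and the method.

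**Conclusion.** The point holds as a modest improvement. Continuous baseline MMDs are absent from the Day 1, PGIC and MBS analyses, and the SAP gives no reason why they could not be used. The cost is precision only: about 1 to 5 power points for Day 1, on assumed baseline distributions, a Day 1 risk proportional to MMDs and relative reductions of 20-30%. For PGIC and MBS the size is unknown and probably smaller; it depends on a correlation the documents do not give. A reader might infer that the planned p-values are biased or that a confirmatory claim is at risk. Neither follows: the tests are valid, and these endpoints are outside the testing strategy. The unspecified Day 1 effect estimate and CI method is a gap whatever the power gain.

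**What to change.** **Day 1 migraine.** Analyse the Day 1 rate with a linear model with robust standard errors containing treatment, MHD stratum and baseline MMDs. It accepts the fractional imputed values. Report the adjusted difference from placebo with 95% CI for each dose, and keep the CMH test as a check.

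**PGIC and MBS.** Put baseline MMDs and baseline MMDs-by-visit where the baseline-score terms were removed. This is the lesser part.

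**Cost.** A few sentences in SAP section 12.5 and a few lines in Appendix IV; no new data. The summary for Day 1 becomes an adjusted risk difference, and the precision caveat in section 12.4.3 about covariates in logistic models does not carry over to a linear model.

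**Timing.** If the blind is already broken, label these analyses supplementary and leave the planned ones in place. The list of changes in protocol edition 3.0 refers to sponsor staff being unblinded after the database lock for the Placebo-controlled Period, so this should be settled first.
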